3.2 Study Objectives

3.2.1 Primary Objective

The co-primary trial objectives are to evaluate the greater efficacy for pain improvement and function improvement of 4 mL Ampion versus saline IA injection when applied to patients suffering from severe OAK. Efficacy will primarily be assessed with WOMAC A pain and WOMAC C function scores.

Mean change in the WOMAC A weekly pain scores from Baseline to Week 12 will be compared between Ampion and saline control. Mean change in WOMAC C function score will be compared between Ampion and saline control. This will ensure that Ampion is superior to saline in improving pain and function.

3.2.2 Secondary Objectives

The secondary trial objectives include the following evaluations of an intra-articular injection of Ampion, as compared to saline, when administered to patients suffering from severe OAK: improvement in pain utilizing a 100 mm Visual Analogue Scale (VAS) scale; assessment of safety; improvement in the Patient Global Assessment; and the amount of rescue analgesia.

3.2.3 Exploratory Objectives

Exploratory objectives include analyzing the effect, if any, of the efficacy of Ampion, as compared to saline, on stiffness; Outcome Measures in Rheumatology Clinical Trials and Osteoarthritis Research Society International (OMERACT-OARSI) responder status; proportion of treatment failures; change in pain and function as a cumulative distribution function (CDF) plot.

Analysis with biomarkers, such as those for analgesic use and chemokines and cytokines associated with inflammation and cartilage regeneration, may be analyzed to compare differences between treatment groups using urine samples collected at Week 12.

Additionally, a Bayesian meta-analysis will be performed for WOMAC A Likert (LK) pain sub score using all KL 4 patients in studies AP-003A, AP-003-B, AP-003-C, AP-004, and AP-013.

3.3 Safety Monitoring Committee

A Safety Monitoring Committee (SMC) will be established to review the safety of Ampion as the study progresses. The SMC will consist of independent clinicians and statisticians not involved in the conduct of the clinical trial. The Medical Monitor will attend open sessions of the SMC meetings. The SMC will be primarily responsible for reviewing any serious Adverse Event (SAE) and other clinically important safety findings (e.g., discontinuations due to AEs) that may occur during the study. Prior to unblinding any treatment assignments, a charter will be developed to detail the SMC review responsibilities, the frequency of meetings, and data evaluation plans.

A promising zone analysis will be run after outcomes are available for 724 patients (70% of final sample size). The promising zone analysis will be run for WOMAC C since function will be the predominant determinant of sample size.

The SMC, with the exclusion of the Medical Monitor, will also be tasked with evaluating whether sample size increase criteria has been met for the interim efficacy analysis. The SMC committee will review the interim analyses and report the next steps to the Sponsor, which will include one of the following prespecified actions: (1) continue to a total of 1,034 patients, 517 patients per study arm, randomized 1:1 for Ampion and saline IA injection; (2) sample size re-estimation up to 1.5 times the original trial size for a total of 1,552 patients, 776 per study arm, randomized 1:1 for Ampion and saline IA injection, has occurred using the promising zone and the new sample size will be reported.

3.4 Stopping Rules

There are no stopping rules for early success stopping. The trial will enroll 1,034 patients, or if the promising zone triggers an expansion, up to 1,552 patients.

The Safety Monitoring Committee may recommend trial termination if there is a safety concern.

3.5 Study Endpoints

3.5.1 Co-Primary Endpoint

The trial will test whether Ampion can produce a superior improvement in pain and function vs. saline control. This goal is achieved using two co-primary endpoints:

Change in the WOMAC A pain sub score between Baseline and Week 12

Change in the WOMAC C physical function sub score between Baseline and Week 12

Mean 12-week change in the WOMAC A weekly pain scores determined at Baseline and Week 12 will be compared between Ampion and saline control. Mean 12-week change in WOMAC C physical function sub score will be compared between Ampion and saline control.

3.5.2 Secondary Endpoints

- Change in PGA between Baseline and Week 12
- Change in the 100 mm VAS Pain scale between Baseline and Week 12
- Use of rescue analgesia (amount of acetaminophen used between Baseline and Week 12)
- Incidence and severity of treatment-emergent adverse events (TEAEs)

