5.1 Description of Study Visits

5.1.1 Visit -1 (Day -28 through Day 0, in-clinic): Screening

The following procedures will be performed:

- Obtain written informed consent before the start of any study specific procedure.
- Review medical history including all previous treatments for OA
- Record prior and concomitant medications including start/stop dates, indication, dose and frequency
- Record demographic data including year of birth, age, gender and race
- Measure and record height and weight
- Perform and record physical examination
- Record KL Grade from radiological assessment that is not older than 6 months prior to screening. Patient may have an x-ray at screening in order to satisfy this requirement
- Record pain in the index knee with the WOMAC Index 3.1 using both the 5-point Likert scale and the 100mm VAS scale
- Record pain in the contralateral knee with the WOMAC Index 3.1 pain subsection using both the 5-point Likert scale and the 100mm VAS scale
- Record vital signs. (Measure body temperature, systolic blood pressure [SBP], diastolic blood pressure [DBP] and pulse rate)
- Evaluate all inclusion and exclusion criteria to ensure that patients meet all inclusion criteria and none of the exclusion criteria
- Review collection instructions of daily diary pain scores with subject

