10.4.2 Secondary Endpoints

- Change in PGA between Baseline and Week 12
- Change in the 100 mm VAS Pain Scale between Baseline and Week 12
- Use of rescue analgesia (amount of acetaminophen used between Baseline and Week 12)
- Incidence and severity of treatment-emergent adverse events (TEAEs)

A serial gatekeeping approach will be used to test the secondary endpoints in a sequential manner (i.e. PGA, 100 mm VAS, rescue analgesia).

The difference between treatment groups in the mean change in PGA from Baseline to Week 12 will be analyzed using a similar MMRM model, with Treatment assignment, Week, and Baseline value as fixed effects and including patient as a repeated measure with a compound symmetric covariance matrix for residuals.

The difference between treatment groups in the mean change in 100 mm VAS from Baseline to Week 12 will be analyzed using a similar MMRM model, with Treatment assignment, and Baseline value as fixed effects and including patient as a repeated measure with a compound symmetric covariance matrix for residuals.

The difference between treatment groups in the amount of acetaminophen used between Baseline and Week 12 will be analyzed with a Wilcoxon rank-sum test.

All secondary efficacy analyses will be reported with one sided p-values and successively compared to a critical level of 0.025 if each preceding test was significant.

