### **3.4 Covariates**

Analyses of change will include treatment assignment, Week, and the Baseline measure of the variable being analyzed as a covariate in the model.

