### 8.6.2 Secondary Effectiveness Endpoints

Secondary effectiveness endpoints will be analyzed using the ITT and the PP analysis populations. All secondary efficacy tests will be performed and reported with one-sided p-values for superiority of Ampion.

Change from Baseline to 2, 4, 6, 8, 10, 12, and 24 weeks for the PGA will be analyzed using a MMRM model. Treatment assignment, Week, and Baseline PGA will be included as fixed effects and a compound symmetric covariance matrix for residuals to reflect the repeated measures.

Change from Baseline to 12 weeks for the 100mm VAS Pain Score will be analyzed using a MMRM model. Treatment assignment, and Baseline PGA will be included as fixed effects and a compound symmetric covariance matrix for residuals to reflect the repeated measures.

Use of rescue analgesia (amount of acetaminophen used) will be compared by treatment arm. A Wilcoxon rank-sum test will be used to compare overall pill count use over the study between saline and Ampion.

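### Rescue analgesia, the last gated secondary endpoint, is compared without baseline adjustment: the test is valid, but it may forgo some precision if tablet use is related to baseline pain

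*Protocol*

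**What the plan says.** Protocol 3.5.2 lists the endpoint among the secondaries: "Use of rescue analgesia (amount of acetaminophen used between Baseline and Week 12"). The order of testing is set in Protocol 10.4.2: "A serial gatekeeping approach will be used to test the secondary endpoints in a sequential manner (i.e. PGA, 100 mm VAS, rescue analgesia"). Each one-sided p-value is "successively compared to a critical level of 0.025 if each preceding test was significant". SAP 8.6.7 gives the same order and opens it only after both co-primary endpoints have succeeded.

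The three gated secondaries are analysed differently:

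- **PGA:** a repeated-measures model with a baseline term. SAP 8.6.2: "Treatment assignment, Week, and Baseline PGA will be included as fixed effects".
- **100 mm VAS:** a repeated-measures model with a baseline term in both documents. SAP 8.6.2 names the PGA baseline for it where Protocol 10.4.2 has the endpoint's own baseline. That looks like a slip, but it is still a baseline covariate.
- **Rescue analgesia:** no covariate and no stratum. Protocol 10.4.2: "The difference between treatment groups in the amount of acetaminophen used between Baseline and Week 12 will be analyzed with a Wilcoxon rank-sum test". SAP 8.6.2: "A Wilcoxon rank-sum test will be used to compare overall pill count use over the study between saline and Ampion".

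The general covariate rule in SAP 3.4 reads: "Analyses of change will include treatment assignment, Week, and the Baseline measure of the variable being analyzed as a covariate in the model". A tablet total is not a change score. The supply is first issued at the Baseline visit (Protocol 5.1.3), so the endpoint has no baseline value of its own and the rule does not reach it. Neither document adds a baseline-adjusted rescue analysis, even as a sensitivity analysis.

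Baseline pain is available. Protocol 10.3.6 defines baseline WOMAC A as the mean of the scores from days -6 to 0, all before the injection.

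**The concern.** How much rescue medication a patient takes may depend on how much pain that patient had at entry. If so, part of the between-patient spread in tablet counts can be predicted from a value the trial already holds. An unadjusted test leaves that part in its error term and is less sensitive than the same data allow. The randomization text (Protocol 3.6 and 10.3.10) names no stratification by baseline pain, so only the analysis could take account of it.

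What is at stake is the power of the last gated test. The validity of that test and the trial's main conclusion are not affected.

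**Working it through.** **Inputs from the documents.** One-sided level 0.025 (Protocol 10.4.2). Allocation 1:1, with 984 evaluable patients out of 1,034 (Protocol 4.1), so 492 per arm. For pain, a difference of 0.83 - 0.62 = 0.21 and an SD of 0.85 (Protocol 4.1). For rescue analgesia the documents give no effect size, spread, sample size or power.

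**Reproducing the plan's own figure.** The only endpoint with full inputs is WOMAC A:

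n per arm = 2 × (1.960 + 1.282)² × (0.85 / 0.21)² = 344.3, rounded up to 345, or 690 in total. This matches the stated 690. Power is 97.2% at 492 per arm and 97.8% at 517 per arm, against a stated 97%. The same normal approximation is used below.

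**Gain from adjustment.** Let r be the correlation between the ranked tablet amount and baseline pain. This is an assumption, because the documents do not give it. Adjustment multiplies the residual variance by 1 - r². Therefore:

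- patient-equivalent gain = 1 / (1 - r²) - 1
- adjusted power = Φ[(1.960 + z) / √(1 - r²) - 1.960], where z = 0.842 if the unadjusted test has 80% power

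For r = 0.3: 1 - r² = 0.91 and the gain is 1/0.91 - 1 = 9.9%. The power is Φ(2.802/0.954 - 1.960) = Φ(0.977) = 83.6%.

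| Assumed r | 1 - r² | Gain in patients | 492 per arm acts like | 80% power becomes |
|---|---|---|---|---|
| 0 | 1.00 | 0% | 492 | 80.0% |
| 0.1 | 0.99 | 1.0% | 497 | 80.4% |
| 0.2 | 0.96 | 4.2% | 512 | 81.6% |
| 0.3 | 0.91 | 9.9% | 541 | 83.6% |
| 0.4 | 0.84 | 19.0% | 586 | 86.4% |
| 0.5 | 0.75 | 33.3% | 656 | 89.9% |

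The 80% starting point is a convention. From 90% the same correlations, 0.1 to 0.5, give 90.3%, 91.1%, 92.5%, 94.3% and 96.3%.

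**Check by simulation.** Skewed tablet counts (negative binomial), 492 per arm, 4,000 runs per setting, with an assumed treatment effect held constant on the log scale:

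| Rank correlation | Wilcoxon power | Rank analysis of covariance |
|---|---|---|
| 0 | 73.9% | 74.0% |
| 0.12 | 73.9% | 74.7% |
| 0.23 | 69.8% | 71.8% |
| 0.33 | 66.8% | 71.4% |
| 0.42 | 61.9% | 69.6% |

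The table should be read across each row. The Wilcoxon column falls because a stronger covariate adds spread while the effect is held constant. With no treatment effect, the rejection rate was about 0.023 to 0.029 over both tests. The Monte Carlo standard error is √(0.025 × 0.975 / 4,000) = 0.0025, so both tests are consistent with 0.025.

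**The case against.** The strongest reply is that nothing is wrong. A rank-sum test in a 1:1 randomized trial of about 1,000 patients is valid, and leaving an endpoint with no baseline value of its own outside SAP 3.4 is coherent. This stands: the point is about efficiency only.

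Several stronger readings are tempting, and the documents do not support them:

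- **That power is certainly lost.** A reader might infer this because the two preceding secondaries are adjusted. The loss depends on a correlation that appears nowhere in the documents. Entry is limited to KL grade 4 with WOMAC A of at least 1.5 on a 0 to 4 scale (Protocol 4.3), and NSAIDs may continue (Protocol 8.3). Both could keep the correlation low, though the documents cannot settle that.
- **That chance imbalance in baseline pain is a second harm.** It is the same unexplained variance seen from another side, and the Wilcoxon test's error rate already allows for it.
- **That rescue is the only gated test described without a baseline term.** For the WOMAC C co-primary, Protocol 10.4.1 and SAP 8.6.1 list Week alone as a fixed effect. The Protocol synopsis, Protocol 10.3.4 and SAP 3.4 supply the baseline term, so rescue stands alone only once those texts are reconciled.
- **That pre-study analgesic use is a second ready-made covariate.** What exists is a medication history (Protocol 5.1.1: "Record prior and concomitant medications including start/stop dates, indication, dose and frequency"), not measured consumption in a run-in period. Turning it into a factor would need a coding rule that the documents do not contain.

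The practical reach is also small. Rescue is the fifth test in line, after two co-primaries, PGA and VAS, and no power was planned for it.

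**Conclusion.** The point holds as an optional, low-cost improvement. The planned test is correct but may be less sensitive than the data allow. The size cannot be taken from the documents and should be quoted only as a range: no gain at zero correlation, about 1% in patient equivalents at 0.1, 4% at 0.2, 10% at 0.3, 19% at 0.4 and 33% at 0.5. From an assumed 80%, that is between 0 and about 10 percentage points of power. At a correlation of about 0.1 or less, the change makes almost no difference.

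The figures assume 492 evaluable patients per arm, the normal approximation, and a roughly linear relation between ranked tablet use and baseline pain. The benefit is realised only if the four tests ahead of rescue analgesia are all significant.

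One related matter is firmer. SAP 8.6.2 counts tablets over the whole study, which runs to Week 24, and rescue use is still reviewed at that visit (Protocol 5.1.12). Protocol 3.5.2 and 10.4.2, and SAP 3.2 and 8.6.7, stop at Week 12. The test needs a single window, whichever form of it is used.

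**What to change.** In Protocol 10.4.2 and SAP 8.6.2, name one test for rescue analgesia: a rank analysis of covariance of the amount of acetaminophen from Baseline to Week 12, with the baseline WOMAC A weekly pain score as the single covariate. Keep the one-sided 0.025 level and the place in the sequence, and report the unadjusted Wilcoxon p-value as supportive. Do not offer a stratified rank test as an alternative or add a medication-history factor: a gated test should leave no choice to the analyst.

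Cite Protocol 10.3.6 for the baseline score, because Protocol 10.3.11.5 starts the averaging window one day earlier. In the same sentence, change the SAP 8.6.2 window to Baseline to Week 12.

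The cost is one sentence in each document and a few lines of code, with no new data, visits or patients. Protocol 10.3.10 foresees a final SAP before unblinding at the interim analysis, which is a natural time for the SAP edit. The downsides are a slightly less familiar test and little return if the correlation is low. SAP 7.2 lists several imputation methods for the tablet count without naming the main one; this edit does not settle that.

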3.5.3 Exploratory Endpoints

- Change in WOMAC B stiffness sub score between Baseline and Weeks 2, 4, 6, 8, 10, 12, and 24

- Response status based on the OMERACT-OARSI criteria at Weeks 2, 4, 6, 8, 10, 12 and 24
- Proportion of treatment failures at Week 12
- Change in pain and function analysis as a cumulative distribution function (CDF) plot
- A Bayesian meta-analysis for LK WOMAC A pain sub score including KL 4 patients from studies AP-003-A, AP-003-B, AP-003-C, AP-004, and AP-013
- Change in WOMAC A pain sub score between Baseline and Weeks 2, 4, 6, 8, 10, and 24
- Change in WOMAC C function sub score between Baseline and Weeks 2, 4, 6, 8, 10, and 24
- Change in WOMAC C function sub score between Baseline and Weeks 2 through 12 and Weeks 2 through 24
- Change in PGA between Baseline and Weeks 2, 4, 6, 8, 10, and 24
- Change in WOMAC C physical function sub score between Baseline and Weeks 2, 4, 6, 8, and 10
- If collected, difference in urine analysis between treatment groups at Week 12

3.6 Blinding and Randomization

Patients will be assigned to treatment by a randomization schedule developed and maintained by an independent statistician. Patients, the investigator, Sponsor, and all study staff having a role in the day-to-day conduct of the study will remain blinded to the treatment assignment.

Ampion and saline will be provided as blinded study vials labeled with the appropriate information. To maintain study blinding, vial labels will be designed to adequately cover vial contents and prevent discrimination between active and placebo. Syringes, needles, and rescue medication (acetaminophen) will be provided to the sites.

A comprehensive presentation of the Data Management Plan (DMP) and Statistical Analysis Plan (SAP) will be approved by Ampio Pharmaceuticals, Inc. prior to unblinding of study data. The SMC will be unblinded to perform the interim analysis.

3.7 Code-breaking

Where required, safety personnel and/or investigator may be unblinded to a particular patient's treatment assignment to meet reporting requirements to Regulators. Unblinding may occur by contacting Ampio Pharmaceuticals, Inc.

4 SELECTION OF PATIENTS

4.1 Number of Patients

This trial will use an adaptive design with promising zone method for sample size re-estimation.

This trial is designed for 1,034 patients, 517 per study arm, randomized 1:1 for Ampion and saline IA injection. There will be an interim analysis at 724 patients, 362 per study arm, randomized 1:1, Ampion and saline.

Following the interim analysis, enrollment will either a) continue up to a total of 1,034 patients, 517 patients per study arm, randomized 1:1 for Ampion and saline IA injection; b) allow for sample size re-estimation up to 1.5 times the original trial size for a total of 1,552 patients, 776 per study arm, randomized 1:1 for Ampion and saline IA injection.

The Ampion effect was estimated as the average change in pain from Baseline to Week 12 for KL 4 subjects receiving Ampion from all prior single injection studies randomized 1:1 with saline control. Saline effect was estimated as the average change in pain from Baseline to Week 12 for KL 4 subjects receiving saline from all prior single injection studies randomized 1:1 for Ampion and saline. The sample size for assessing the WOMAC A Pain score alone would be 690 total patients for 90% power.

The Ampion effect was estimated as the average change in function from Baseline to Week 12 for KL 4 subjects receiving Ampion from all prior single injection studies randomized 1:1 with saline control. Saline effect was estimated as the average change in function from Baseline to Week 12 for KL 4 subjects receiving saline from all prior single injection studies randomized 1:1 for Ampion and saline. The sample size for assessing the WOMAC C Function score alone would be 984 patients for 90% power.

The total sample size is chosen as the larger of the two values. To be conservative sample sizes were estimated with a 5% dropout so 1,034 patients will be enrolled to achieve 984 total patients. All ITT patients will be included in the statistical analysis. At the assumed effect size there is a 90% probability of success at 1,034 patients.

The study design of 1,034 total patients achieves 97% power assuming a WOMAC A pain score with mean pain decreases of -0.83 for Ampion and -0.62 for saline and a standard deviation of 0.85.

As described in Section 10, a Promising Zone method will be employed for a sample size re-estimation and the trial may increase to 1,552 patients.

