3 STUDY DESIGN

3.1 Study Design Overview

This is a randomized, saline-controlled, double-blind study with a 28-day screening period for each patient followed by a 24-week participation period. This trial will use an adaptive design with promising zone method for sample size re-estimation at the interim analysis. Daily assessments of WOMAC A pain using a subject diary will be assessed for seven days beginning one week prior to the clinic visits at Week 0 (baseline) and Week 12 to allow for calculation of a WOMAC A weekly pain score, which will be used for conducting the primary efficacy analysis.

This trial is designed for 1,034 patients, 517 per study arm, randomized 1:1 for Ampion and saline IA injection. There will be an interim analysis at 724 patients, 362 per study arm, randomized 1:1, Ampion and saline. After the interim analysis, enrollment will either a) continue up to a total of 1,034 patients, 517 patients per study arm, randomized 1:1 for Ampion and saline IA injection; b) allow for sample size re-estimation using the promising zone method (Pocock, 2011) up to 1.5 times the original trial size for a total of 1,552 patients, 776 per study arm, randomized 1:1 for Ampion and saline IA injection.

The clinical effects of treatment on severe OAK will be evaluated at baseline 2, 4, 6, 8, 10, 12, and 24 weeks, using the Western Ontario and McMaster Universities Arthritis Index (WOMAC[®]) osteoarthritis Index 3.1, and the Patient's Global Assessment of disease severity (PGA).

The WOMAC[®] and PGA are validated scoring systems and sets the standard for the patient response. In order not to bias the collection of data, only questions from the validated WOMAC Index 3.1 and the PGA will be asked of patients.

The trial has co-primary hypotheses and requires success on both for a successful trial. First, pain reduction must be demonstrated for Ampion vs. saline control. Next, a function improvement must be shown on Ampion vs. saline control.

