10.3.4 Statistical Analysis of Co-Primary Effectiveness Endpoints

A mixed-effects model with repeated measures (MMRM) will be used to test the main effect of change in WOMAC A weekly pain score (determined as the average of Daily Pain measurements taken at Baseline and Week 12) from Baseline of Ampion vs. saline at 12 weeks. The model will include change from Baseline measures at 2, 4, 6, 8, 10, and 12 weeks. Treatment assignment, week, and Baseline WOMAC A measure will be included as fixed effects. Patient ID will be included to capture repeated measures using a compound symmetric covariance matrix for residuals. The primary hypothesis test for pain is the change in pain at 12-weeks at the one-sided $\alpha = 0.025$ level.

The same model will be used to test the effect of WOMAC C function change from Baseline of Ampion vs. saline at 12 weeks. WOMAC C will be tested at one sided $\alpha = 0.025$. Because both endpoints have to achieve statistical significance, this pairing ensures the one-sided Type I error control at the 0.025 level.

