10.3.5 Primary Hypotheses

The trial has co-primary hypotheses – requiring success on both for a successful trial. First, pain reduction must be demonstrated for Ampion vs. saline control. Next a function improvement must be shown on Ampion vs. saline control.

Reduction in Pain, as measured by a change in the WOMAC A pain sub score as measured by the 5-point Likert scale between Baseline and Week 12, will be greater in patients treated with Ampion than with saline:

- Null Hypothesis: $\mu_A = \mu_S$
- Alternate Hypothesis: $\mu_A < \mu_S$

Where μ_A = mean pain reduction in Ampion arm; μ_S = mean pain reduction in saline arm. Lower mean change scores indicate greater pain reduction.

Improvement in function, as measured by a reduction in the WOMAC C function sub score as measured by the 5-point Likert scale between Baseline and Week 12, will be greater in patients treated with Ampion than with saline:

- Null Hypothesis: $\mu_A = \mu_S$
- Alternate Hypothesis: $\mu_A < \mu_S$

Where μ_A = mean function reduction in Ampion arm; μ_S = mean function reduction in saline arm.

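### The 90% probability of success in Protocol 4.1 and SAP 2.4 is the power for WOMAC C alone; the joint power for both co-primaries is not reported

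*Protocol*

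**What the plan says.** Protocol 4.1 and SAP 2.4 size each co-primary separately. For pain: "The sample size for assessing the WOMAC A Pain score alone would be 690 total patients for 90% power". For function: "The sample size for assessing the WOMAC C Function score alone would be 984 patients for 90% power". The larger number is taken and raised for 5% dropout, so that 1,034 are enrolled to yield 984. Both sections then state that all ITT patients enter the analysis, and conclude: "At the assumed effect size there is a 90% probability of success at 1,034 patients". A separate sentence covers pain: "The study design of 1,034 total patients achieves 97% power". Its inputs are mean changes of -0.83 (Ampion) and -0.62 (saline), with a common SD of 0.85.

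The success rule is stated elsewhere. Protocol 3.1: "The trial has co-primary hypotheses and requires success on both for a successful trial". Protocol 10.3.5 and SAP 4.1 repeat it ("requiring success on both for a successful trial"). Protocol 10.3.4 tests each endpoint at one-sided 0.025 and relies on the both-must-win rule for error control: "this pairing ensures the one-sided Type I error control at the 0.025 level".

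**The concern.** The 90% belongs to one endpoint at one sample size. The next step in the text presents it as the chance that the trial succeeds, which is a different event. When two tests must both be significant, the probability of success cannot exceed the power of the weaker one, and it falls below that unless the weaker endpoint's success always carries the other with it.

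The both-must-win rule protects the type I error but costs power, and the sample-size section does not account for that cost. What is at stake is the accuracy of the plan's main design property. The tests, the alpha and the decision rule are not affected.

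**Working it through.** **Inputs from Protocol 4.1 and 10.3.4.** Pain difference 0.83 − 0.62 = 0.21; SD 0.85; one-sided alpha 0.025 (z = 1.960); 1:1 allocation; 690 total for pain and 984 for function, each at 90% power (z = 1.282); 1,034 enrolled.

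**Not in the documents.** The WOMAC C effect and SD, and the correlation ρ between the two test statistics. I back-solve the first as a standardised effect and show a range for the second. With two arms and the same patients on both endpoints, ρ is approximately the within-arm correlation between the pain and function changes.

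**1. Reproduce the plan's figures** (normal approximation for two means).
- Pain: d = 0.21/0.85 = 0.2471. n per arm = 2(1.960 + 1.282)²/0.2471² = 344.3, so 345 per arm and 690 in total, as stated.
- Pain power = Φ(d√(n/2) − 1.960). At 492 per arm: Φ(3.875 − 1.960) = 97.2%. At 517 per arm: Φ(3.972 − 1.960) = 97.8%. The stated 97% fits 984 slightly better than 1,034.
- Dropout: 984 × 1.05 = 1,033.2, which gives the stated 1,034.
- Function: the standardised effect implied by 90% at 492 per arm is 3.2415/√246 = 0.2067. Power is then 90.0% at 984 by construction, and Φ(3.323 − 1.960) = 91.4% at 1,034.

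So the stated 90% reproduces as the power of WOMAC C alone at 984.

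**2. Joint power, fixed design.** P(Z_A > 1.960 and Z_C > 1.960), with the two statistics bivariate normal and correlation ρ. At ρ = 0 it is the product: 0.900 × 0.972 = 0.875 at 984, and 0.914 × 0.978 = 0.893 at 1,034.

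| ρ (assumed) | 984 evaluable | 1,034 with full information |
|---|---|---|
| 0 | 0.8750 | 0.8934 |
| 0.3 | 0.8797 | 0.8970 |
| 0.5 | 0.8845 | 0.9008 |
| 0.7 | 0.8907 | 0.9059 |
| 0.8 | 0.8945 | 0.9090 |
| 0.9 | 0.8983 | 0.9122 |
| 1 (limit) | 0.9000 | 0.9135 |

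For any form of dependence, the lower bound is 0.900 + 0.972 − 1 = 87.2% at 984 and 0.914 + 0.978 − 1 = 89.1% at 1,034 (the latter from unrounded powers).

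**3. With the promising-zone increase.** I took a simulation of the Protocol 10.3.9 rule: re-estimation on WOMAC C to 90% conditional power within the zone, the stated cap, a conventional final test, and all sizes scaled by 492/517 to the evaluable basis. Joint success was 90.1% (ρ = 0), 91.1% (0.5) and 91.9% (0.8). This describes a design that can grow to 1,552, so it is not a figure at 1,034.

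**The case against.** The best defence is that the sentence is made at 1,034 patients and directly follows the statement that all ITT patients are analysed. On that basis joint power is 89.3% to 91.4%, and 90% is correct from a correlation of about 0.5. Patients who miss Week 12 still contribute earlier visits to the MMRM and to the imputation, so 984 understates the information. If half of what dropout removes were recovered (an assumption; 1,009 effective patients), joint power would be 89.3% at ρ = 0.5 and 90.2% at 0.8. Pain and function are subscales of one instrument, answered by the same patient about the same knee, so a correlation near zero is implausible. The section is also fairly open: each size is marked as being for one endpoint alone, and the reader is told that the larger was taken.

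Most of this stands, and it limits the size of the point. It does not supply the missing derivation. The plan enrols 1,034 because it expects 984, and imputation does not fully restore lost Week 12 data. On the full-1,034 reading WOMAC C alone would have 91.4%, so 90% would match the joint power only if the correlation happened to be near 0.5, a value stated nowhere.

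A reader might infer that the 90% is simply overstated, or that the trial is too small. The documents support neither. Whether the figure is too high depends on the information basis and the correlation, and the documents do not settle either.

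**Conclusion.** The point holds as a labelling and reporting gap of minor severity. The 90% is single-endpoint power for WOMAC C at 984 evaluable patients, and the probability of trial success is not derived in either document.

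At 984, joint power is below 90% for any correlation short of 1. The gap is 2.5 points at correlation 0, about 1.6 at 0.5, and 0.9 down to 0.2 at 0.7 to 0.9, which I regard as a plausible range for two subscales of one questionnaire (an assumption). At 1,034 with full information there is no shortfall from a correlation of about 0.5 upward.

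These figures rest on the normal approximation, on a WOMAC C effect back-solved from the plan's own 984, and on a two-sample comparison rather than the baseline-adjusted MMRM.

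**What to change.** In Protocol 4.1 and SAP 2.4:
- Label 90% as the power for WOMAC C alone and 97% as the power for WOMAC A alone, and say for each whether it is at 984 or 1,034.
- Replace the probability-of-success sentence with the joint power for both co-primaries at the fixed size, naming the correlation used. The sponsor can estimate it from the KL 4 patients in the prior single-injection studies. These already supply the effect estimates, and Protocol Table 1.2 lists both WOMAC A and WOMAC C for all four. The sponsor's own estimate should be printed, not the illustrative range above.
- Report any figure that includes the promising-zone increase separately, with its assumptions.

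The cost is a few sentences in each document and one short calculation. The headline figure may become slightly less favourable. Sample size, alpha, tests and decision rule stay as they are.
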